### **MRI Scan I**

All subjects who are eligible will undergo a structural scan, using a Siemens 3T Trio, followed by an fMRI scan that involves alcohol cue exposure. Female participants will be asked to take a

pregnancy test free of charge and must have a negative result in order to continue with participation in the study. Female participants may opt out of the urine pregnancy test and sign a waiver (one of the standard INC MRI scanning forms) indicating they understand that the risks associated with MRI and unborn fetuses is unknown and that they are confident that they are not currently pregnant.

The research assistant will go over the contraindications for fMRI screening form again with the participant to ensure that eligibility has not changed since the phone screen; if there is any question that a participant might not be safe to go into the scanner the appointment will be cancelled and rescheduled if possible.

Prior to going into the MRI scanner, the MRI technologist on duty will ask participants to remove all jewelry and metal objects from their pockets. Participants will be required to change into scrubs to prevent any possible risk from metallic objects or decorations in their clothing. Eligible participants will be escorted to a changing room where they will be asked to change into the hospital scrubs provided, and to lock up their belongings in the locker.

A trained MRI technician will position participants in the scanner and ensure that all safety procedures are followed. In an MRI scan, the subject lies down on a table and is placed into a long donut-shaped magnet. A specially designed coil will be placed around the head to provide better images (as is done with standard clinical examinations). As the MRI scan is performed, the subject will hear loud rattling and knocking noises that are normal for a MRI scan.

During the scanning session, we will acquire anatomical images for subsequent analysis as well as functional images during an alcohol cue task. The alcohol cue task compares the taste of an individual's favorite alcoholic beverage with a sweet, appetitive control taste (litchi juice). Subjects will be administered 1 ml of each beverage through Teflon tubing that is attached to a computer controller gustometer, over each 24-second trial. The total amount of the alcoholic beverage is only 1 ml (less than a teaspoon).

After the scan, a research assistant will escort the participants back to the changing room where their belongings are locked. Subjects in this group will be given their MBRP or RP condition assignment after the scan is complete in order to minimize any expectancy effects that may occur as a result of knowing their condition assignment before all pre-treatment measures have been taken. Subjects will be compensated \$30 for completion of the MRI scan I appointment.

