## ***MRI and Connectivity:***

### **MRI Data Collection (Baseline and Week 32).**

Before treatment begins and at the 6 month follow-up appointment (week 32), subjects will participate in an fMRI cue exposure session (Claus et al., 2011). Participants who are determined eligible to have an MRI scan will undergo a structural scan, using a Siemens 3T Trio, followed by a functional MRI scan that involves alcohol cue exposure. Our cue procedure is consistent with NIAAA guidelines and less risky than previous studies that have examined this mechanism in a sample receiving treatment (e.g., Myrick et al., 2008; Spagnolo et al., 2014; see protection of human subjects section). **Structural MRI (sMRI):** We will acquire a high-resolution protocol sufficient to permit accurate tissue classification and anatomical parcellation. For optimal contrast between gray matter (GM), white matter (WM) and cerebral spinal fluid (CSF) at 3T, we will use a multi-echo MPRAGE (MEMPR) sequence with the following parameters: TR/TE/TI = 2300/2.74/900 ms, flip angle = 8°, FOV = 256x256 mm, Slab thickness = 176 mm, Matrix = 256x256x176, Voxel size = 1x1x1 mm, Number of echos = 4, Pixel bandwidth = 650 Hz, Total scan time = 6 min. **Functional MRI (fMRI) – Cue-Elicited BOLD:** fMRI scans will be collected with single-shot full k-space echo-planar imaging (EPI) with ramp sampling correction using the intercommissural line (AC-PC) as a reference (TR: 2.0 s, TE: 27ms,  $\alpha$ : 70°, matrix size: 64 × 64, 32 slices, voxel size: 3 × 3 × 4 mm^3). Image-based higher order automatic shimming will be employed. FMRI data will be acquired with a 32-channel coil. Scanner instability and signal-to-noise ratio during fMRI scanning on a phantom will be monitored weekly throughout the project period. Automated analysis of scanner instability with the Weiskoff method is routinely performed. We have used our alcohol cue task successfully in over 600 individuals (Claus et al., 2011). It is reliable and well validated. The task compares the taste of an individual's favorite alcoholic beverage with a sweet, appetitive control taste (litchi juice). The task was designed to minimize movement by only administering 1 ml of each beverage through Teflon tubing that is attached to a computer controller gustometer, over each 24 second trial. It is important to note that the total amount of the alcoholic beverage is only 12 ml (less than a teaspoon). The task itself involves a block design with twelve pseudorandomly ordered alcohol and control trials that are presented in two consecutive runs. In order to examine whether the effects of MBRP differ from those of RP, we will calculate the signal change for alcohol minus the control condition in the precuneus, putamen, and anterior cingulate and use the signal in these regions of interest (ROIs) in the structural equation models (see analysis section).

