### **Criteria for inclusion in the study are:**

1. Must be between the ages of *21 and 60* and provide informed consent;
2. Have a primary DSM-V diagnosis of alcohol use disorder;
3. Must be within 10 days of last drink;
4. Must have been drinking heavily (criteria dependent upon individual's age, gender, and BMI) for a consistent period of time;
5. Must have a breath alcohol level of 0 at screening (to sign consent form);
6. Not currently taking any medications for the treatment of psychiatric disorders, including substance use disorders, mood disorders, and psychosis;
7. Female subjects must not be pregnant, as indicated by a pregnancy test which will be administered at baseline (tests will be re-administered at the 32 week session prior to the MR scan);
8. Must not be positive for sedatives, opiates, cocaine, or amphetamine on drug screen at baseline;
9. Must not meet criteria for psychotic disorder, bipolar disorder, or a major depressive episode;
10. Must not have a Beck Depression Inventory (BDI) score of more than 28 (29-63 indicates severe depression);
11. Must not rate 2 or higher on BDI question 9 (assessment of suicidality);
12. Must have a Clinical Institute Withdrawal Assessment (CIWA) score less than 8 (indicating no need for medical detox). If CIWA is greater than 8, patient will be referred to detox and only accepted into study after detox is successfully completed.
13. Must have expressed a desire during their initial screen to reduce the number of drinks they regularly consume

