### **Physical Risks and Discomforts.**

- Participants who could suffer potential risks include those with metal implants (pacemaker, metal rods, bone screws, orthodontics, metal flakes from metalworking). Participants are carefully screened for these types of metal implants or any other bodily exposure to metal during informed consent, and again prior to the MR scan, using an MRI safety screening checklist. It will be clearly explained to participants that the magnetic field of the MR environment has the potential to cause burns or bodily injury if ferrous metal objects are implanted in the body, or if personal articles containing ferrous material are brought into the environment. MR Facility rules strictly forbid staff from entering the magnet room carrying metal objects.
- Female participants will be warned that the risk of MRI to pregnant women and fetuses is currently unknown. Study staff will explicitly inform all female participants of this fact and they will be given the option to complete a free urine pregnancy test. Female subjects who test positive will not be allowed to participate in the study. The pregnancy test will be strongly recommended by the study staff. If the participant wishes to dismiss the request to complete a urine pregnancy test, they must sign an agreement to acknowledge the risk and indicate that they do not believe they are currently pregnant. This will be required immediately prior to the MRI scan.
- Participants will be informed about potential discomfort they may experience due to scanner noise. This risk will be minimized by providing participants with earplugs and headphones. Ultimately, the volume of the noise is not great enough to pose a health risk, with or without earplugs/headphones.
- Participants will be told that they may experience discomfort from lying in one position for a long time. The discomfort should subside once the scan is complete, but some subjects may be sore for a more extended duration.

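### The pregnancy test is mandatory in inclusion criterion 7 and at Scan II, yet a woman may decline it by signed waiver at Scan I

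*Combined protocol and SAP*

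**What the plan says.** Four places in the combined protocol and SAP set the rule.

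- **Section VI, Criteria for inclusion, item 7:** "Female subjects must not be pregnant, as indicated by a pregnancy test which will be administered at baseline". The item adds that the test is repeated at week 32 before the scan. It mentions no waiver.
- **Section XI, MRI Scan I:** women are asked to take a "pregnancy test free of charge and must have a negative result in order to continue with participation in the study". The next sentence reads: "Female participants may opt out of the urine pregnancy test and sign a waiver". The form is described as "indicating they understand that the risks associated with MRI and unborn fetuses is unknown" and "that they are confident that they are not currently pregnant". It is identified as a standard form of the imaging facility.
- **Section XI, Follow-up Assessment II and MRI Scan II:** a second test is requested, and a negative result is needed to enter the scanner. No opt-out is stated.
- **Section XVI, Management of Risks, Physical Risks and Discomforts:** the test is offered as an option that staff strongly recommend. Then: "If the participant wishes to dismiss the request to complete a urine pregnancy test, they must sign an agreement to acknowledge the risk" and state that they do not believe they are pregnant. This is tied to the time just before the MRI scan, without saying which scan. The same bullet excludes from the study any woman who tests positive.

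The scan session includes the alcohol cue task, in which the participant tastes her favourite alcoholic drink. Section XV, Physical Risks and Discomforts, describes the risk of MRI to a fetus as unknown.

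**The concern.** Item 7 makes the test itself the evidence of eligibility. The opt-out replaces that evidence with the woman's belief about her own status. A woman with an unrecognised pregnancy would hold that belief sincerely and sign the form. She would then be scanned and given a taste of alcohol, although the plan intends to exclude her and does not claim to know the fetal risk of the scan. What is at stake is a bypassed safeguard, and a procedure that breaches an eligibility criterion when staff follow it as written.

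**Working it through.** No arithmetic applies. The check is a comparison of the texts for each scan.

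| | Negative test required, no exception | Test may be declined |
|---|---|---|
| Scan I | Inclusion item 7 | MRI Scan I procedure (explicit); Management of Risks (general wording) |
| Scan II | Inclusion item 7 (week 32 repeat); Scan II procedure | Management of Risks only (general wording, Scan II not named) |

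1. **Scan I.** Taken alone, the MRI Scan I paragraph can be read as a rule followed by its exception. Item 7 carries no such exception. A woman who uses the waiver is scanned without the test that item 7 names, so the conflict is between sections and remains on either reading of that paragraph.

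2. **Scan II.** The text specific to that visit agrees with item 7. The only contrary text is the general bullet in Management of Risks. It refers to the MRI scan without limiting itself to the first, so whether the opt-out extends to week 32 is ambiguous.

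3. **Can the other safeguards find an unrecognised pregnancy?**
   - Phone or online screening against the inclusion criteria relies on self-report.
   - Repeating the contraindication form before the scan, with cancellation if there is any doubt about safety, can catch a suspected pregnancy or one disclosed at that point. It cannot catch one the woman does not know about.
   - Telling every woman that the fetal risk is unknown, and strongly recommending the test, should reduce the number who decline. Neither step tests those who do decline.

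4. **Consequence of a positive test.** Management of Risks excludes the woman from the study. The Scan II procedure only keeps her out of the scanner. At Scan I the first rule fits item 7. At week 32, after treatment has ended and at the last main assessment, the two texts differ.

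5. **How many women?** The plan does not state how many women will be scanned, how many are expected to decline, or how many positive tests are expected. No count can be derived.

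**The case against.** The strongest reply is that the opt-out is deliberate and disclosed. It follows directly after the requirement, uses a standard facility form, and reappears in the risk-management section. It also fits section XIX, under which giving each physiological measure is voluntary. Staff recheck contraindications on the day and cancel if in doubt. This much stands: the opt-out is a policy and not a slip, and the surrounding steps narrow the gap. It does not remove the conflict with item 7, and voluntariness does not oblige the study to scan a woman who declines the test.

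A reader might infer four stronger things that the documents do not support.

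- **That the alcohol is a material hazard in itself.** The volume is small on either figure the plan gives (1 ml in the MRI Scan I procedure, 12 ml under MRI Data Collection). Participants must have been drinking heavily and be within 10 days of their last drink. The point rests on the bypassed test.
- **That week 32 staff face two plainly opposed rules.** Management of Risks never names Scan II. The visit-specific text requires a negative result and can reasonably be read as governing.
- **That women are not warned about alcohol in pregnancy.** The waiver and consent forms are not in the documents, so nothing can be said about their content.
- **That trial results are affected.** Heavy drinking days come from the Timeline Follow Back and need no scan.

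**Conclusion.** The point holds as a minor safety and consistency issue. Item 7 and the Scan II procedure require a negative test without exception. The Scan I procedure, and the general wording in Management of Risks, allow a signed statement of confidence in its place. An unrecognised pregnancy could therefore be scanned, with a small alcohol taste, against the plan's own criterion. The opt-out is explicit for one scan and ambiguous for the other.

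The conclusion rests on the wording of the protocol alone and on no assumed rate of pregnancy or refusal. It applies only to in-person scanning, because the remote COVID-19 version collects no MRI data, and it becomes live again when the original procedures resume. It has no effect on the heavy drinking days analysis, the planned 226 participants or Aim 1 power.

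**What to change.** 1. In MRI Scan I, delete the opt-out sentence. In Management of Risks, Physical Risks and Discomforts, delete the wording that makes the test optional, recommends it and lets it be declined.
2. State one rule for both scans in those sections and in the Scan II procedure: *A negative urine pregnancy test on the day is required before the scan and its alcohol cue task; a woman who declines is not scanned and continues as an MRI-ineligible participant, as described under Baseline Session.*
3. In Management of Risks, limit exclusion from the study after a positive test to Scan I. At week 32 a positive test then bars only the MRI, as the Scan II procedure already says.

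The cost is small. The free test is already listed at both scan visits, so no test or visit is added. The non-MRI route exists, opting out of the scan is already allowed (section XVI, Exposure to Alcohol), and at Scan I the woman has not yet been told her assignment. The loss is the scans of women who decline, which would reduce the imaging data for Hypotheses 3 and 4. Their number is unknown, so no loss of precision is quoted.

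One limit remains: item 7, read literally, still asks for a test from a woman who declines and stays in the trial unscanned. She receives neither the scan nor study alcohol, so what is left is a matter of eligibility wording, not exposure.

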## **Goal-setting Session**

Subjects will have a 1-hour individual session with a trained therapist before starting the 8-week long program, resulting in a total of 9 individual therapy sessions. The purpose of this being a chance for the participant to discuss with their therapist their goals for the next 8 weeks in terms of drinking reduction goals or abstinence goals. Subjects will take a BAC test before the session starts.

## **MBRP (or RP) Weekly Sessions**

Subjects will meet with a trained therapist for 1-hour individual therapy sessions once a week for 8 weeks at the CINC in a private consultation room.

Subjects will be breathalyzed and complete their check-in survey before every session starts. If subjects are dropped due to accumulated "missed" sessions due to failure to follow the abstinence instructions, they will not be compensated for previous attended therapy sessions. They will be informed of this contingency during the phone screen, consent visit and is stated the consent form.

Subjects will be compensated \$15 for each therapy session they complete (payment for each completed session is given to participants at week 8).

### **Intermediate Session (4 weeks)**

At the intermediate session, subjects will continue with their usual session with a therapist (including a BAC test), and either before or after their appointment, complete a set of self-report outcome measures, and provide a blood sample. Subjects will be compensated \$30 for completion of this session.

